#### **D.2.f. Retention**

Staffing will be funded by the study to reach patients after hours. Incentives will be provided for completing the follow-up HbA1c at the 12 and 24 week visits. Patients will be contacted at pre-arranged times, with up to 3 attempts during the week of the encounter. In the event of failure to contact, a letter/email will be sent and staff will then reach out to the patient designated secondary contacts. The medical records will be monitored at OSU and queries to the patient's designated primary care physician will be made up to 24 weeks following enrollment.

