#### **D.2.g. Program Completion**

Participants will receive an order to complete the HbA1c at 12 and 24 weeks at any OSU lab. A reminder letter will be sent 1 week prior to the date and a phone call reminder will occur 2 days before the visit. Study team will complete the 12 week and 24 week call and search the electronic medical record and primary provider's chart for HbA1c and healthcare utilization at 12 and 24 weeks.

**E. Study Drug:** Patients in both groups will be provided standard of care insulin therapy throughout the study, including insulin glargine (TOUJEO® U300) plus additional background therapy (non-insulin and prandial insulin therapies), based upon discharge team preference. The starting dose will be determined during hospitalization from the dose of glargine/detemir U100 in a 1:1 dose conversion. Upon discharge, standard titration instructions (every 4 days) will be implemented in the DOS group but will be left to the discretion of the discharge team in the ESC group.

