#### H.1.a. Missing Data

All data analyses will be completed as intention to treat analyses (i.e., individuals analyzed by group according to original random assignment, without regard to adherence to the intervention).

Longitudinal outcomes (e.g., HbA1c) will be analyzed using mixed models utilizing all available measurements from individuals randomized. Missing binary outcomes (e.g., accurate and complete discharge orders, adherence) and missing covariate data will be imputed, using multiple imputation in SAS v9.3 PROC MI.

Table 9. Study Procedures and Visits

Visit number	0	1	2	3	4
Time of Visit	Screen/consent	2 week	6 week	12 week	24 week
Type of visit	In-person	Phone	Phone	In-person	In-person
Informed consent/contact team	x				
Randomization	x				
Load DOS into EMR and inform discharge team	x				
Provide study drug and glucose monitoring instructions	x				
Demographics/Socioeconomic status	x				
Diabetes history	x				
Hospitalization history	x				
PSS scale	x				
DES-SF	x			x	x
Newest Vital Sign	x				
Glucose/insulin diary	x				
Review DOS		x			
Ascertain health care utilization		x	x	x	x
Review glucose/insulin diary		x	x	x	x
Hypoglycemia/Hyperglycemia		x	x	x	x
Review insulin adherence, persistence		x	x	x	x
Nurse counsellor (DOS group only)		x	x	x	x
HbA1c	x			x	x
Fasting blood glucose	x			x	x

DOS=discharge order set, EMR=electronic medical record, PSS=Perceived Social Support scale, DES-SF=Diabetes empowerment scale-short form, In-Person clinic visits will be conducted at either CarPoint East or McCampbell Hall

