### H.2.a. Statistical Power and Sample Size

The sample size for our study was based on a comparison of change in HbA1c over three months adjusting for baseline covariates related to change in HbA1c: age, whether or not patient is new to insulin, and dose of insulin; the first two were selected based on our preliminary data and the latter was selected based on an expected relationship. The following expression, adapted from Oakes and Feldman, was used to calculate the number of individuals per group:

$$n/group = \frac{4\sigma^2(1-\rho)(1-R^2)(Z_{1-\alpha/2} + Z_{1-\beta})^2}{\Delta^2}$$

where  $\sigma$  is the standard deviation of HbA1c,  $\rho$  is the correlation between baseline and 24 week HbA1c levels,  $R^2$  is the proportion of variability in change in HbA1c explained by the baseline covariates,  $\Delta$  is the difference in change in HbA1c between treatment groups, and  $Z_{1-\alpha/2}$  and  $Z_{1-\beta}$  are standard normal quantiles calculated at the two-sided type-I error rate ( $\alpha$ ) and power (1- $\beta$ ). Using parameter values based on our preliminary data ( $\sigma = 2.2\%$ ,  $\rho = 0.25$ ,  $R^2 = 0.5$ ) and based on the effect observed by Wexler ( $\Delta = 0.8\%$ ), we will need 89 individuals per treatment group with 24 week follow-up to achieve 80% power at  $\alpha = 0.05$ . Since we expect 20% attrition, we will recruit 111 individuals per group into our study. The study is powered to detect a difference in the primary endpoint only. However, additional secondary endpoints of strong interest are pre-specified and included in the analysis.

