**Secondary:**

- Difference in the change in HbA1c from baseline to 12 weeks (+/-2 weeks) post-discharge (%, mmol/l)
- Difference in the change in HbA1c from baseline to 12 and 24 weeks (+/-2 weeks) post-discharge (%, mmol/l)
- Difference in the change in fasting plasma glucose (FPG) from baseline to 12 and 24 weeks in DOS vs ESC (mg/dl)
- Difference in the % of patients achieving HbA1C 7% in DOS vs ESC (12, 24 weeks)
- Difference in the % of patients achieving HbA1C 6.5% in DOS vs ESC (12, 24 weeks)
- Difference in the % of patients achieving individualized HbA1C target in DOS vs ESC (12, 24 weeks)
- Difference in the proportion of patients with accurate and complete discharge orders for basal insulin and related supplies. (%)
  - Assessed as complete dose, quantity dispensed, adequate refills (separate for basal and prandial insulin), and correct prescription for pen needles (presence, quantity, adequate refills), no jargon
- Difference in the proportion of patients with accurate and complete discharge orders for prandial insulin and related supplies. (%)
  - Assessed as complete dose, clear dosing instructions, quantity dispensed, adequate refills, and correct prescription for pen needles (presence, quantity, adequate refills), no jargon
- Difference in the proportion of patients with a discharge prescription for glucose monitoring supplies (%)
- Difference in adherence to glargine U300 (% taking >80% of doses) at 2, and 24 weeks
- Difference in the proportion of patients who remain on glargine U300 at 24 weeks (%)
- Difference in the mean dose of glargine U300 at 2 and 24 weeks (units)
- Difference in the frequency of glucose monitoring at 2 and 24 weeks (times per day)
- Difference in the proportion of patients who follow up with their primary care provider or endocrinologist within 2, 6 weeks of discharge (%)
- Difference in the incidence of documented symptomatic (BG <54 mg/dl) hypoglycemia (%)

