#### H.2.d. Secondary Aims:

- Determine whether DOS is associated with lower HbA1c at 12 months compared to ESC.
- Determine whether the DOS in conjunction with nurse supported self-titration of basal insulin glargine U300 is associated with improved persistence with insulin therapy, adequate dose titration, and use of self-monitored blood glucose.
- Determine whether the DOS is associated with improved discharge instructions and processes of care for insulin-requiring patients. This will be measured in terms of clarity of instructions, adequacy and completeness of prescriptions for insulin and diabetes supplies, and follow-up plan.

Each of these secondary outcomes will be binary (e.g., adequate vs. inadequate dose titration). Missing values of the outcomes will be imputed using treatment group and baseline covariates. The difference in proportions between treatment groups will be computed for each data set and the results will be combined using Rubin's rules to obtain a final two-sample test of proportions.

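### Missing 24-week adherence and persistence outcomes are to be imputed from arm and baseline covariates, leaving out the 2, 6 and 12-week data that the trial collects

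*Combined protocol and SAP*

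**What the plan says.** H.2.d gives the only stated list of imputation predictors for secondary outcomes: "Missing values of the outcomes will be imputed using treatment group and baseline covariates". The completed data sets are then compared by a difference in proportions and pooled with Rubin's rules.

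H.1.a sets the scope and the software (PROC MI) but names no predictors: "Missing binary outcomes (e.g., accurate and complete discharge orders, adherence) and missing covariate data will be imputed". Adherence is thus named as an imputed outcome. For continuous longitudinal outcomes such as HbA1c, the same section instead uses mixed models on all available measurements.

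In Table 9 the row "Review insulin adherence, persistence" is marked at 2, 6, 12 and 24 weeks, and HbA1c at baseline, 12 and 24 weeks.

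The secondary endpoints in H.2.b include adherence to U300 at 2 and 24 weeks, "Difference in the proportion of patients who remain on glargine U300 at 24 weeks", and the proportions reaching HbA1c 7%, 6.5% and an individualised target at 12 and 24 weeks.

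H.2.a plans for missing data: "Since we expect 20% attrition".

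**The concern.** A patient reached at week 2, 6 or 12 and then lost leaves information about the 24-week outcome. A model with only arm and baseline ignores it. Someone who reported non-adherence at week 12 would be imputed as adherent at week 24 at about the rate of patients in the same arm with similar baseline values.

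This is valid if dropout is random given arm and baseline. It is biased if dropout also depends on the interim adherence or control, although the data that would address this are already in hand. Post-discharge contact differs by arm (Table 7: nurse titration calls in DOS, coordinator calls in ESC), so dropout could relate to interim status differently in the two arms. The documents do not show that it will.

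At stake are the 24-week binary secondary endpoints. Discharge-order endpoints, 2-week adherence and early follow-up visits gain nothing from later interim data and are outside this point.

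**Working it through.** **1. The plan's own figures.** H.2.a gives SD 2.2, baseline to 24-week correlation 0.25, R² 0.5 and difference 0.8. The formula gives n = 4 × 2.2² × 0.75 × 0.5 × (1.960 + 0.842)² / 0.8² = 89.04, and 89/0.8 = 111.25. These match the stated 89 and 111. About 111 − 89 = 22 patients per arm would have an imputed 24-week outcome.

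**2. Information left out.** With correlation 0.25, baseline HbA1c explains 0.25² = 6% of the variance of 24-week HbA1c. Take the baseline to 12-week correlation as 0.25 as well, and let r be the 12 to 24-week correlation. With both values as predictors, R² = (0.0625 + r² − 2 × 0.0625 × r)/0.9375. This is 27% for r = 0.5 and 64% for r = 0.8. Both values of r are assumptions.

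**3. Adherence, closed form.** Assumed: true adherence 60% (ESC) and 70% (DOS) at both 12 and 24 weeks, 12 to 24-week phi 0.2 to 0.6, uninformative baseline, 20% missing held in each arm, and a dropout risk ratio of 32/12 = 2.67 between the 12-week adherence groups. Imputation from arm alone then returns the observed proportion, so bias in an arm = phi × (12-week adherence among those retained − true 12-week adherence).

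- Non-adherent patients drop out more. ESC dropout is 12% (adherent) and 32% (not), so retained adherence is 0.6 × 0.88/0.80 = 0.660 and the bias is 0.060 × phi. DOS dropout is 13.3% and 35.6%, so retained adherence is 0.7 × 0.867/0.80 = 0.758 and the bias is 0.058 × phi.
- Reversed. ESC retained is 0.6 × 0.733/0.80 = 0.550, bias −0.050 × phi. DOS retained is 0.7 × 0.754/0.80 = 0.660, bias −0.040 × phi.

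Estimated difference (true 10 points) as phi goes from 0.2 to 0.6:

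| Who drops out | Dependence in ESC only | Both arms | DOS only |
|---|---|---|---|
| Non-adherent | 8.8 to 6.4 | 10.0 to 9.9 | 11.2 to 13.5 |
| Adherent | 11.0 to 13.0 | 10.2 to 10.6 | 9.2 to 7.6 |

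With 89 per arm, SE = √((0.6 × 0.4 + 0.7 × 0.3)/89) = 7.1 points. The largest one-arm bias is 3.6/7.1 = 0.5 SE, and the largest shared-dependence bias is 0.6/7.1 = 0.1 SE.

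**4. HbA1c below 7%, if the rule applies.** Inputs from H.2.a: SD 2.2, correlation 0.25, difference 0.8, 20% missing. Assumed: 24-week means 9.5 and 8.7 (12.8% and 22.0% below 7%, true difference 9.2 points), the same means and SD at 12 weeks, joint normality, r = 0.5 or 0.8, odds ratio of missingness 1.5, 2 or 3 per SD of 12-week HbA1c, and every dropout having a 12-week value. Logistic imputation on baseline within arm, by numerical integration, gives:

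| Who drops out | Dependence in ESC only | Both arms | DOS only |
|---|---|---|---|
| Poorly controlled | 8.5 to 7.1 | 9.5 to 10.4 | 10.2 to 12.5 |
| Well controlled | 10.0 to 12.9 | 8.9 to 8.0 | 8.1 to 4.3 |

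Simulated trials of 111 per arm with 20 imputations give an SE of about 5.1 to 5.9 points. The worst cases are (12.5 − 9.2)/5.77 = 0.57 SE and (9.2 − 4.3)/5.33 = 0.9 SE. Both need r = 0.8 and odds ratio 3 in DOS only. With shared dependence the largest bias is 1.2 points, about 0.2 SE. If half of the dropouts leave at random before week 12, the ranges narrow to 8.1–8.8, 9.4–9.9 and 9.7–11.0, and reversed to 9.6–11.5, 8.6–9.0 and 6.3–8.6 (same column order).

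Adding the 12-week value returns 9.1 to 9.3 in every scenario. That follows from the set-up, in which dropout depends only on 12-week HbA1c. It does not show protection against dropout driven by later events.

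**The case against.** - **Scope.** A reader might infer that the plan says outright that the HbA1c targets are imputed from arm and baseline. It does not. The H.2.d list contains no HbA1c target. The rule reaches those endpoints only because it is the sole imputation rule stated and H.1.a covers missing binary outcomes generally. H.2.d also does not say that no other predictor may be used.
- **Definition of persistence.** H.2.d speaks of persistence with insulin, H.2.b of remaining on U300. A patient who reports stopping U300 at week 12 may already count as not having remained on it, in which case nothing is missing. The concern applies to that endpoint only if it means status at week 24, which H.2.b leaves open.
- **Recovery from records.** D.2.f provides record monitoring, and queries to the primary care physician "will be made up to 24 weeks following enrollment". D.2.g adds a search of the record and the provider's "chart for HbA1c and healthcare utilization at 12 and 24 weeks". Section A.1.b (Sources of Materials) lists medication adherence among the outcomes and allows outpatient records to be requested. Section I expects easier access for patients followed in the health system. Missingness may therefore be lower than modelled.
- **Size.** The larger biases need strong dependence in one arm only. A reader might infer that the secondary results will be materially biased, or biased towards DOS. The documents say nothing about who drops out, so neither inference is supported.

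All four limit reach and size. None supplies a reason to leave the interim data out of the imputation model.

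**Conclusion.** The point holds as an inexpensive improvement to the analysis of secondary endpoints. It is direct for persistence and 24-week adherence, conditional for remaining on U300, and inferred for the HbA1c targets. Bias arises only if dropout depends on interim adherence or control beyond arm and baseline, and its direction is unknown. Under the assumed scenarios it is about 0.2 SE or less with shared dependence, and at most about 0.6 SE (poorly controlled patients dropping out) or 0.9 SE (well controlled patients dropping out) with strong dependence in one arm. The 12 to 24-week correlations, dropout models, HbA1c means and adherence rates are all assumptions. The primary test and the sample size are untouched, and H.2.a says that the study is powered for the primary endpoint only.

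**What to change.** In H.2.d:

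1. Impute within arm, and add the 2, 6 and 12-week adherence and persistence reports when imputing 24-week adherence and U300 status. Imputing by arm also allows for the different staff who make the early calls. State whether remaining on U300 means status at week 24.
2. Impute continuous 24-week HbA1c within arm from baseline and 12-week HbA1c, using predictive mean matching or a transformation if residuals are not normal. Derive the 7%, 6.5% and individualised targets from it, and state that the rule covers those H.2.b endpoints.

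The cost is SAP wording, slightly larger imputation models and a distributional assumption for HbA1c. No new data are needed.

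Two separate drafting corrections in the same section add nothing to the point above. The statement that every secondary outcome there is binary should be limited to the endpoints that H.2.b defines as proportions: the list it follows begins with HbA1c, and H.2.b also has fasting glucose, U300 dose and monitoring frequency on their own scales. The twelve-month HbA1c aim should be reconciled with the 12 weeks given under Secondary Aims and in H.2.b.

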#### **D.2.d. Enrollment and Randomization**

Enrollment is expected at a rate of approximately 3 patients per week with the last patient enrolled within 18 months to allow completion and analysis of all data within 3 years. The study and all study-related documents will be approved by the OSU IRB. Written informed consent will be obtained. Patients will be stratified by pre-admission insulin therapy (yes/no) and randomized using a random number generator program.

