Based upon preliminary data, we found that approximately 30% were of African American race. We are enrolling a wide age range, 25-75, in order to achieve optimal external validity, but have excluded the younger and older participants due to insufficient numbers in those ranges and possibly different educational needs, that may involve people (family) other than the patient. Participants are anticipated to be sick and have other comorbidities (in our pilot data, 70% were admitted for a problem that was not directly related to diabetes). However, all participants will be free-living in the community and have a phone. Due to bias introduced by additional support staff at institutions such as nursing homes and rehabilitation centers, these participants will be excluded. Participants who are unable to provide consent in English will be excluded as this number is very small and will hinder motivational interviewing (MI) process. Other vulnerable populations, such as prisoners will be excluded. Pregnant individuals will be excluded since the HbA1c is not as reliable and because such individuals have different motivations and follow-up already in place.

Permission will be obtained from the attending physician of the admitting inpatient service prior to approaching participants for enrollment. Randomization will be conducted using a computerized random number generator program that is weighted and will be stratified by race. The frequency of telephone follow-up is felt to be adequate to establish reasonable endpoints for reinforcement of behavior and capture a realistic window for readmission.

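### The binary secondary-aim outcomes are compared without the randomisation stratum; the crude test is valid, but a stratified risk difference would give a modest gain in precision at no cost

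*Combined protocol and SAP*

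**What the plan says.** Section H.2.d covers persistence with insulin, dose titration, use of self-monitored glucose and discharge processes, and treats these outcomes as binary. Baseline data enter at the imputation step: "Missing values of the outcomes will be imputed using treatment group and baseline covariates". The comparison itself is crude: "The difference in proportions between treatment groups will be computed for each data set", and the results are pooled by Rubin's rules "to obtain a final two-sample test of proportions". Neither a stratum nor a covariate appears in that test.

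The allocation is described in two places, which disagree on the factor. Section D.2.d says: "Patients will be stratified by pre-admission insulin therapy (yes/no) and randomized using a random number generator program". Human Subjects A.1.a says: "Randomization will be conducted using a computerized random number generator program that is weighted and will be stratified by race". Neither gives a block size or any other scheme for balancing the arms within strata.

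Section H.2.c adjusts the primary HbA1c model for age, new-to-insulin status and insulin dose, and gives precision as the reason. The synopsis adds that outcomes will be examined by pre-admission therapy, among other factors. That describes a subgroup look, not adjustment of the treatment comparison.

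**The concern.** A factor used to stratify randomisation is normally carried into the analysis. Where stratification balances the arms on a factor that predicts the outcome, the crude standard error still counts the between-stratum variation that the design has removed. Intervals are then wider than they need be and tests reject less often than their nominal level. Where the design does not enforce balance, adjusting for a prognostic factor still makes the estimate more precise.

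The plan accepts this reasoning for the primary endpoint and drops it for the binary outcomes without explanation. Section H.2.a says the study is powered for the primary endpoint only, so precision matters most for the secondary outcomes. They also carry weight in reporting: section J plans one manuscript on discharge processes and a second that includes titration and persistence.

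**Working it through.** **The plan's own figure.** The only sample-size calculation is for the primary endpoint (section H.2.a). With σ = 2.2, ρ = 0.25, R² = 0.5, Δ = 0.8, two-sided α = 0.05 and 80% power:

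n per group = 4 × 2.2² × 0.75 × 0.5 × 7.849 / 0.8² = 89.04, against 89 stated. Then 89 / 0.8 = 111.25, against 111 stated.

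This reproduces and is not affected by the present point. The plan gives no rates and no power for the binary outcomes, so everything below is an assumption range.

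**Size of the effect with balanced strata.** Take two equal strata with outcome rates p₁ and p₂ and mean rate p̄. The crude variance uses p̄(1−p̄). With allocation balanced within strata, the relevant variance is the mean of p₁(1−p₁) and p₂(1−p₂). The ratio of the two is the overstatement, and the true size of a nominal 5% test is 2 × [1 − Φ(1.96 × √ratio)].

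| Rates in the strata | Gap (points) | Variance ratio | Standard error too large by | True size |
|---|---|---|---|---|
| 40% and 40% | 0 | 0.2400 / 0.2400 = 1.00 | 0% | 5.0% |
| 30% and 50% | 20 | 0.2400 / 0.2300 = 1.04 | 2% | 4.5% |
| 20% and 50% | 30 | 0.2275 / 0.2050 = 1.11 | 5% | 3.9% |
| 20% and 60% | 40 | 0.2400 / 0.2000 = 1.20 | 10% | 3.2% |

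For uncommon outcomes with smaller gaps the ratio stays near 1: 5% and 10% give 0.069375 / 0.06875 = 1.009, and 5% and 15% give 0.0900 / 0.0875 = 1.029.

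**Unequal strata.** In the pilot (section C.2.b, Table 2), 26 of 58 type 2 patients (45%) were on insulin at admission. With stratum share w = 0.45, overall rate p = 0.50 and gap g, the ratio of true to nominal standard error is √(1 − w(1−w)g² / [p(1−p)]). For gaps of 0, 10, 20, 30 and 40 points the crude standard error is too large by 0%, 0.5%, 2.0%, 4.8% and 9.0%. The equal-strata table is therefore a fair guide if the trial resembles the pilot in this respect.

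**Simulation.** The settings were 111 per arm, w = 0.45, no missing data and 15,000 trials per cell. The pooled z test was compared with the Cochran-Mantel-Haenszel (CMH) test. Power is for a 19-point treatment difference.

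| Gap (points) | Blocks of 4 in strata: crude type I error | Blocks: power, crude / CMH | Simple randomisation: crude type I error | Simple: power, crude / CMH |
|---|---|---|---|---|
| 0 | 5.3% | 81.4% / 81.4% | 5.1% | 80.9% / 80.6% |
| 20 | 4.7% | 82.6% / 83.1% | 5.4% | 81.5% / 82.6% |
| 30 | 4.0% | 82.9% / 84.7% | 5.2% | 80.9% / 84.5% |
| 40 | 3.5% | 84.1% / 88.1% | 5.0% | 80.9% / 87.6% |

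The simulation error on a 5% rate is √(0.05 × 0.95 / 15,000) = 0.18 points, so the departures from 5% under simple randomisation are noise or close to it. With blocks, stratifying the analysis corrects the standard error. With simple randomisation the crude test is already correctly sized, and stratifying makes the estimate itself more precise. In both cases the power gain is about 1 point or less at a 20-point gap.

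**Is the factor prognostic?** The pilot speaks to this only for change in HbA1c (section C.2.b, Table 3): any insulin on admission 0.95 (SE 0.40, p = 0.02), new to insulin −1.51 (SE 0.45, p = 0.002), baseline HbA1c −0.64 (SE 0.22, p = 0.006). African American race was not predictive (0.32, SE 0.46, p = 0.49). Nothing is reported for persistence, titration, glucose monitoring or discharge orders.

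**The case against.** The strongest reply is that nothing here is invalid. A crude risk difference is simple and unbiased under randomisation, the test does not inflate false positives, and the study claims power for the primary endpoint alone. All of that stands.

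Three stronger readings are tempting, and the documents support none of them.

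- A reader might infer that the reported standard errors are necessarily too large and that the tests run at about 3.9%. This needs balance within strata, which neither account of randomisation states; the word weighted in A.1.a does not establish it. The figure also needs an assumed 30-point gap.
- A reader might infer a definite loss of 4% to 20% in variance. Those figures correspond to assumed gaps of 20 to 40 points. No document supports a particular gap, and the range has to include zero. If race is the factor used, the pilot gives no sign that it matters even for HbA1c.
- A reader might infer that every binary endpoint is affected alike. H.2.d lists particular aims. The HbA1c-target endpoints appear in H.2.b and are not explicitly assigned this test. Completeness of discharge orders is produced by the discharge team and the order set, so a patient-level stratum may predict it hardly at all.

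It can also be said that baseline covariates are already used in the imputation. That is true, but it does not adjust the comparison. Imputing with covariates that the analysis leaves out can itself make Rubin's variance somewhat conservative.

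What survives is narrower. The plan stratifies, collects the predictors and argues for precision on the primary endpoint, yet leaves the same benefit unused on outcomes for which it claims no power.

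**Conclusion.** The point holds as a matter of efficiency, not validity. If arms are balanced within strata, the crude comparison is conservative to the extent that the factor predicts the outcome. If they are not, it is correctly sized and only precision is given up.

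On the assumed rates, the variance overstatement runs from 0% to about 20%, and the power at stake runs from nothing to about 4 points with blocked strata, or about 7 points with simple randomisation. A 20-point gap sits at the low end of both. These sizes rest on assumed stratum rates, a stratum share borrowed from the pilot and complete data. The case is best supported for the HbA1c targets, because the pilot predictors concern HbA1c. It is plausible but undocumented for persistence and titration, and weak for discharge-order completeness. The sample size and the primary analysis are unchanged. This is a free improvement with a modest gain.

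**What to change.** 1. Make D.2.d and Human Subjects A.1.a agree on the stratification factor, and state whether allocation is blocked within strata.
2. In H.2.d, replace the crude comparison: within each imputed data set, estimate the risk difference stratified by the factor actually used at randomisation, by a Mantel-Haenszel risk difference or by a logistic model with standardisation. Pool estimates and variances by Rubin's rules. Include the same factor in the imputation model.
3. State that the HbA1c-target endpoints in H.2.b are analysed by the same method, with baseline HbA1c added. This calls for the logistic form with standardisation.

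The treatment effect stays on the risk-difference scale. The cost is a few sentences in the plan and a few lines of code, with no new data and no change in sample size. Fixing the adjustment in advance also removes any later choice between crude and adjusted results.
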